4 STUDY DESIGN

The proposed study is a phase 1, open label, single arm study to evaluate the safety, pharmacokinetics and antiviral activity of single intravenous infusions of 3BNC117-LS and 10-1074-LS in viremic HIV-infected individuals. (Figure 4, Study Design).

Figure 4: Study Design

Ten eligible participants will be enrolled sequentially in the study and will receive each mAb, dosed at 30 mg/kg intravenously and in sequence on study day 0. Following mAb administration, study participants will return for safety assessments on days 1 and 3, and weeks 1, 2, 3 and 4 following dosing, then bi-weekly or monthly until the end of study follow up as indicated in the Time of Events Schedule (**Appendix A**). All participants will be followed for 24 weeks after 3BNC117-LS and 10-1074-LS administration.

Safety assessments will be performed at multiple time points following 3BNC117-LS and 10-1074-LS infusions. Serum samples for PK measurements will be collected before and at the end each mAb infusion administration and at multiple subsequent time points during study follow up, as indicated in the Time of Events Schedule (**Appendix A**). Samples will also be collected for measurement of HIV-1 plasma RNA levels before 3BNC117-LS and 10-1074-LS infusions (screen and day 0) and at every follow up visit. T cell subsets will also be monitored during study follow up. Assessments will also include measurement of ADA responses and sequencing of plasma envelope before infusions and after viral rebound (first time point after viremia nadir is reached and VL is $> 1,000$ copies/ml).

Participants will be advised and encouraged to start ART within 4 weeks of receiving 3BNC117-LS and 10-1074-LS infusions or sooner if: VL fails to decrease by $>0.5 \log_{10}$ copies/ml within 2 weeks of antibody infusions, VL increases $> 0.5 \log_{10}$ copies/ml between weekly measurements or significant T-cell decline (confirmed CD4+ T cells < 200 cells/ μ l) is noted. Participants with current CD4 counts > 300 cells/ μ l will be eligible to enroll in the study. Studies with the unmodified 3BNC117 and 10-1074 in the same study population used the same criterion for entry and showed that CD4 counts remained stable during follow up prior to ART initiation (Caskey, Klein et al. 2015, Caskey, Schoofs et al. 2017) (Bar-On et al. 2018). We have maintained the same criterion in this study to facilitate enrollment, given the overall favorable safety profile seen in the previous studies using similar cutoff. To account for the possibility of transient CD4 count fluctuations in participants who have starting CD4 counts of about 300 cells/mm³, we selected 200 cells/mm³ as the cutoff to re-initiate ART sooner than 4 weeks. The selected CD4 count levels might delay initiation of ART by 1 or 2 weeks, compared to using a slightly higher cutoff. It is also unlikely that participants will experience an accelerated decline in CD4 counts in the course of 4 weeks from antibody infusions that would pose significant additional risk of poor outcomes, such as

development of opportunistic infections. However participants will be closely monitored during this period.

5 STUDY POPULATION

5.1 Inclusion Criteria

1. Males and females, >18 years of age.
2. Confirmed HIV-1 infection.
3. Off ART for at least 4 weeks with a HIV-1 plasma RNA level between 500 and 125,000 copies/mL (ART-naïve or off ART due to intolerance or by choice).
4. Current CD4+ T cell count > 300 cells/ μ l.
5. Participants who can become pregnant and are engaging in sexual activity that could lead to pregnancy agree to use two effective methods of contraception (i.e. condom with spermicide, diaphragm with spermicide, hormone-eluting IUD, hormone-based contraceptive with condom) from 10 days prior to and six months after 3BNC117-LS and 10-1074-LS administration.
6. Participants who can impregnate a partner and are engaging in sexual activity that could lead to pregnancy agree to use barrier protection from 10 days prior to and six months after 3BNC117-LS and 10-1074-LS administration to avoid impregnating a partner who can get pregnant.
7. Willingness to use barrier protection during sexual activity while not on ART to decrease the risk of HIV transmission to a partner at risk for HIV infection.

5.2 Exclusion Criteria

1. Have a history of AIDS-defining illness within 3 years prior to enrollment.
2. History of systemic corticosteroids, immunosuppressive anti-cancer, or other medications considered significant by the trial physician within the last 6 months.
3. Any clinically significant acute or chronic medical condition (such as autoimmune diseases), other than HIV infection, that in the opinion of the investigator would preclude participation.
4. Hepatitis B or C infection as indicated by the presence of Hepatitis B surface antigen (HBsAg) or hepatitis C virus RNA (HCV-RNA) in blood.
5. Laboratory abnormalities in the parameters listed below:
 - Absolute neutrophil count \leq 1,000 cells/ μ l;
 - Hemoglobin \leq 10 gm/dL;
 - Platelet count \leq 100,000 cells/ μ l;
 - ALT \geq 1.5 x ULN;
 - AST \geq 1.5 x ULN;
 - Alkaline phosphatase \geq 1.5 x ULN;
 - Total bilirubin $>$ 1.25 x ULN;
 - eGFR $<$ 60 mL/min/1.73m².
6. Pregnancy or lactation.
7. Any vaccination within 14 days prior to mAb infusions, except for influenza vaccine.

8. Receipt of another investigational product currently or within the past 12 weeks, or expected concurrent participation in another study in which investigational products will be administered.
9. Receipt of any experimental HIV vaccine or anti-HIV monoclonal antibody therapy in the past.
10. History of severe reaction to a vaccine or drug infusion or history of severe allergic reactions.
11. Individuals with known hypersensitivity to any constituent of the investigational products.

6 METHODS AND PROCEDURES

6.1 Screening Procedure and Study Visits

The Time of Events Schedule summarizes the frequency and timing of various study assessments. See **Appendix A**. At the Cornell site, recruitment, screening, and follow up visits during the study period will be performed either at the Weill Cornell Medical Center (WCMC), and antibody infusions will occur at the Rockefeller University Hospital (RUH). At the RU and UPENN sites, all study procedures will occur at the RUH or at the Center for Human Phenomic Science (CHPS) at the Perelman Center for Advanced Medicine (PCAM) of the Perelman School of Medicine University, respectively.

6.1.1 Pre-Screening Questionnaire

Potential participants will first undergo pre-screening by telephone to assess medical history and qualification for the study. Potential participants will have the opportunity to discuss the study and ask questions of the study recruiter at this time. Those who are eligible and interested in participation will attend a screening visit at the RUH, WCMC, or UPENN McGregor Outpatient Clinics.

6.1.2 Screening Visit

Initial Screening Visit:

Study personnel will answer any questions about the study. Written informed consent will be obtained prior to conducting any study procedures. To ensure informed consent, the principal investigator or designee will discuss the following processes individually with each potential participant:

1. Risk-reduction counseling including safer sex (including discussion of sexual activity that could lead to HIV transmission) and pregnancy avoidance counseling;
2. One must assume that no improvement in control of HIV infection will occur given the experimental nature of the monoclonal antibodies;
3. That sexually active males and females, participating in sexual activity that could lead to pregnancy, should use two reliable forms of contraception for 10 days prior to and six months following 3BNC117-LS and 10-1074-LS administration.

If the potential participant consents to participate, site personnel will:

- Perform complete medical history (including review of concomitant medications);

- Perform a general physical examination including height, weight, vital signs (pulse, respiratory rate, blood pressure and temperature), examination of skin, respiratory, cardiovascular and abdominal systems;
- Collect blood and urine specimens for all tests as indicated in the Time of Events Schedule (**Appendix A**);
- Perform a pregnancy test for all female volunteers of child-bearing potential.

If the initial screening visit occurs more than 49 days prior to the date of 3BNC117-LS and 10-1074-LS administration, only laboratory tests (blood and urine specimens) will be repeated and a review of the medical history will be performed.

HIV-1 infected participants that do not meet eligibility criteria due to HIV viral load levels outside of the range specified in the protocol will be independently counseled regarding their HIV care. Participants will be counseled and encouraged to initiate therapy and referrals to HIV providers will be provided, if needed.

6.1.3 Study Drug Administration Visit

Prior to administration of the investigational product(s), site personnel will:

- Review the informed consent form administered at the screening visit with the participant;
- Answer any questions about the study;
- Review interim medical history (including concomitant medications);
- Review safety laboratory data;
- Perform a directed physical examination including weight, vital signs (pulse, respiratory rate, blood pressure and temperature) and any further examination indicated by history or observation;
- Collect blood and urine specimens for all tests as indicated in the Time of Events Schedule (**Appendix A**);
- Perform pregnancy and safer sex counseling;
- Perform a serum pregnancy test for all female volunteers of child-bearing potential and obtain results prior to drug infusion.
- Perform baseline assessment and record any systemic symptoms;
- 3BNC117-LS and 10-1074-LS will be prepared for administration according to **Appendix C**;

Antibody Administration:

- 3BNC117-LS will be administered via a peripheral vein over 30 minutes. The IV line will be flushed with normal saline after all the contents of the infusion bag are administered.
- 10-1074-LS will be administered after 3BNC117-LS infusion is completed and the line is flushed with normal saline. It will also be administered via a peripheral vein over 30 minutes. The IV line will be flushed with normal saline after all the contents of the infusion bag are administered.
- If participants develop grade 3 acute infusion reaction, an immediate hypersensitivity reaction or a life-threatening event during study drug administration, the infusion will be

discontinued and will not be reinitiated (see Section 6.1.7.1). If the acute infusion reaction occurs during 3BNC117-LS infusion, 10-1074-LS infusion will not be infused.

- Participants will be observed for adverse reactions at the study site for 1 hour after the end of the 10-1074-LS infusion. Presence or absence of adverse events will be recorded at 1 hour post infusion.
- Vital signs (pulse, respiratory rate, blood pressure and temperature) will be monitored before administration, at the end of each infusion, 30 minutes (+/- 10min) post final infusion, and at 1 hour (+/- 10 min) post final infusion;
- Rescue medications, including acetaminophen, diphenhydramine (or an alternative antihistaminic) and glucocorticoids will be available in the RUH or at the Center for Human Phenomic Science (CHPS) at the Perelman center for advanced Medicine (PCAM) of the Perelman School of Medicine University for use if clinically indicated.

6.1.4 Post-Study Drug Administration Visit

Participants will be followed through study week 24.

At these follow up visits the following will be conducted:

- Review of interim medical history and use of concomitant medications;
- Perform a symptom-directed physical examination if symptoms are present;
- Local and systemic solicited and unsolicited adverse events will be assessed;
- Pregnancy and safer sex counseling;
- Vital Signs;
- Collect blood and urine specimens for all tests as indicated in the Time of Events Schedule (**Appendix A**);
- In case of adverse event(s), the participant will be assessed and followed up by the clinical team. Supplemental visit(s) for further investigation can be planned at the discretion of the principal investigator or designee. Supplemental visit(s) may be recommended if clinically indicated or to clarify observations.

Specific procedures to be performed at each follow up visit for all study groups are illustrated in the Time of Events Schedules (**Appendix A**).

Any abnormalities (adverse events) including laboratory abnormalities, should be subsequently followed until the event or its sequelae resolve or stabilize.

6.1.5 Final Visit/Early Termination Visit

Assessments will be undertaken according to the Time of Events Schedule (**Appendix A**).

6.1.6 Discontinuation of Study Drug Infusions and/or Participant Withdrawal from Study

6.1.6.1 Discontinuation of Study Drug Infusion

Antibody intravenous infusion will be discontinued for any of the following reasons:

1. Grade 3 acute infusion reactions that occur during infusion.
2. Any immediate hypersensitivity reaction (such as urticarial rash; bronchospasm; laryngeal edema; anaphylaxis; syncope).
3. Life threatening medical event during 3BNC117-LS or 10-1074-LS infusion.

6.1.6.2 Withdrawal from the Study (Early Termination)

Participants may be withdrawn from the study permanently for the following reasons:

1. Participants may withdraw from the study at any time if they wish to do so, for any reason.
2. Following an adverse event at the discretion of the investigator (or designee).
3. Request of the primary care provider if s/he thinks the study is no longer in the best interest of the participant.
4. Participant judged by the investigator to be at significant risk of failing to comply with the protocol in a manner that might lead to harm to self or seriously interfere with the validity of the study results.
5. At the discretion of the FDA or investigator.

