3.12 Outcomes

Primary Outcomes:

- The occurrence of treatment-related solicited and unsolicited grade 3 and serious adverse events (including confirmed laboratory abnormalities).
- The pharmacokinetic profile (including: peak concentrations, half-life, area under curve and clearance rate) of 3BNC117-LS and 10-1074-LS, when administered intravenously and in combination to viremic HIV-infected individuals.
- The decline in plasma HIV-1 RNA level after 3BNC117-LS plus 10-1074-LS intravenous infusions in viremic HIV-infected individuals through week 4 after infusions.

Secondary Outcomes:

- Proportion of individuals with treatment-induced ADA against each mAb and magnitude of the response.
- The rate of adverse events and confirmed laboratory abnormalities that occur during the study follow up period after 3BNC117-LS and 10-1074-LS administration.

Exploratory Outcomes:

[figure not shown]
- Time until return of viremia to baseline levels in participants, who elect to remain off ART after 4 weeks.
- Decline in plasma viremia after antibody infusions across 3BNC117-LS and 10-1074-LS IC₅₀ and IC₈₀ cut points determined by PhenoSense assay or other assays (e.g. bulk PBMC cultures or Q2VOA followed by TZM/bl assay).
- Phenotypic and genotypic analysis of baseline and escape viruses that might arise after single infusions of 3BNC117-LS and 10-1074-LS in viremic HIV-infected individuals.
- Proportion of participants with reduction in half-life or antiviral activity concomitant with ADA.
- Relationship of adverse events to ADA.
- Frequency and magnitude of HIV-1 specific T cell responses and serum neutralizing activity against a multi-clade panel of HIV-1 pseudoviruses, following 3BNC117-LS and 10-1074-LS infusions.
- Gene expression profiles by single RNA sequencing of HIV-1 infected CD4+ T cells.

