7.1 Regimen

- 3BNC117-LS and 10-1074-LS will be administered intravenously, in sequence, at 30 mg/kg (each mAb) once.

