7.4 Assessment of Participant Adherence with Study Product

Not applicable. Participants will be administered 3BNC117-LS and 10-1074-LS at the study sites on study day 0.

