8.4 Participant Enrollment and Follow-Up

The total number of evaluable participants in the study will be 5 to 10.

An over-enrollment of 2 participants will be allowed if participants drop-out prior to week 4. Participants who are discontinued from the study due to AEs will not be replaced. Additional participants will be enrolled after study withdrawal is confirmed. If a participant drops out after receiving 1 or both study drugs, he/she will be invited to return every 4 weeks, for at least 3 months after antibody infusion, for safety monitoring only.

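### Section 6.1.6.2 allows full study withdrawal after an adverse event although all drug is given on day 0, so later PK and ADA data can be lost selectively in participants with events

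*Combined protocol and SAP*

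**What the plan says.** Section 6.1.6.2 opens with "Participants may be withdrawn from the study permanently for the following reasons" and lists five grounds. Item 1 is the participant's own choice. Item 2 reads "Following an adverse event at the discretion of the investigator (or designee", with no condition on grade, relatedness or safety need. Item 3 is a primary care provider's request, item 4 is expected non-compliance, and item 5 is "At the discretion of the FDA or investigator".

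Dosing is confined to one day. Section 7.1 states "3BNC117-LS and 10-1074-LS will be administered intravenously, in sequence, at 30 mg/kg (each mAb) once", and Section 7.4 states "Participants will be administered 3BNC117-LS and 10-1074-LS at the study sites on study day 0". Stopping an infusion has its own list in Section 6.1.6.1: "Antibody intravenous infusion will be discontinued for any of the following reasons".

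Four provisions govern what happens afterwards:
- Section 6.1.6.3 follows the event that caused withdrawal until it resolves or stabilizes, and asks for termination-visit procedures if the participant is willing.
- Section 8.4 invites anyone who drops out after one or both drugs to four-weekly visits for three months or longer, limited to safety. It adds: "Participants who are discontinued from the study due to AEs will not be replaced".
- Section 8.1 defines the safety population by dosing, not by completed follow-up.
- Section 4 plans 24 weeks of follow-up for everyone.

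Among the outcomes in Section 3.12, the PK profile (including half-life, AUC and clearance) and the HIV-1 RNA decline through week 4 are primary. ADA frequency and magnitude are secondary. "Relationship of adverse events to ADA" is exploratory.

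**The concern.** After both infusions are complete there is no study treatment left to stop. Withdrawal from the study then ends scheduled data collection and research procedures, and nothing else. Item 2 makes that depend on having had an adverse event, so the missing data are related to the safety outcome by design.

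The outcomes exposed are those that need late serum: elimination half-life, AUC and clearance, ADA, and the relation of events to ADA and to exposure. They need samples from the very people who may be withdrawn. In the macaque study in Section 3.2.3, one of six animals given the combination lost antibody between weeks 4 and 6, with emerging anti-10-1074-LS responses. A similar pattern in a participant withdrawn at week 4 could be missed. Section 8 gives no rule for missing PK, ADA or RNA data.

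The protocol elsewhere keeps dosed participants under observation. A participant who becomes pregnant after dosing is followed to study end and delivery (Section 6.1.6.3). When dose-limiting toxicities halt enrollment, monitoring continues (Section 15.8). Section 15.1 asks for reports of such toxicities after week 12, a period the safety-only visits in Section 8.4 do not guarantee.

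**Working it through.** **Inputs.** N = 5 to 10 (Section 8.2). Follow-up 24 weeks = 168 days (Section 4). Expected half-lives 70 days for 3BNC117-LS and 90 days for 10-1074-LS (Section 8.2). Parental half-lives in viremic people 9.6 and 12.8 days, and an LS extension of about 3-fold (Section 8.2). Half-life SD up to 6.5 days (Table 3). SD of RNA decline 0.7 log10 (Table 4).

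**1. The plan's own figures reproduce.**
- Table 3 is 1.96 × SD/√n. At SD 6.5: 1.96 × 6.5/√10 = 4.03 and 1.96 × 6.5/√5 = 5.70 days (plan: 4.0 and 5.7).
- Table 4 is a one-sample t-test, two-sided 0.05, 80% power. The effect size times 0.7 gives 0.697, 0.747, 1.177 and 1.490 for n = 10, 9, 5 and 4 (plan: 0.70, 0.75, 1.18 and 1.49).

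**2. Share of the sample.** One participant is 1/10 = 10% to 1/5 = 20%.

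**3. What a week-4 withdrawal leaves of the PK profile.** Fraction remaining at day t = 0.5^(t/half-life).

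| Half-life (days) | Source | Remaining at day 28 | Half-lives seen by day 28 | Half-lives seen by day 168 |
|---|---|---|---|---|
| 70 | Section 8.2 | 0.758 | 0.40 | 2.40 |
| 90 | Section 8.2 | 0.806 | 0.31 | 1.87 |
| 28.8 (3 × 9.6) | assumption | 0.510 | 0.97 | 5.83 |
| 38.4 (3 × 12.8) | assumption | 0.603 | 0.73 | 4.38 |

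The last two rows apply the plan's 3-fold factor to the parental viremic values, since the trial enrolls viremic people. In every row less than one half-life has been observed by week 4, so the terminal slope is poorly determined. Peak concentration and the early part of the curve are still observed.

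**4. If that participant's half-life cannot be estimated.** The Table 3 margin at SD 6.5 goes from 4.03 to 1.96 × 6.5/√9 = 4.25 days (n = 10 to 9), or from 5.70 to 1.96 × 6.5/√4 = 6.37 days (n = 5 to 4).

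**5. HIV-1 RNA.** The primary virologic window closes at week 4, so a withdrawal at week 4 costs it nothing. If an earlier withdrawal made the participant unusable for that outcome, Table 4 gives a detectable decline rising from 0.70 to 0.75 (n = 10 to 9) or from 1.18 to 1.49 log10 copies/ml (n = 5 to 4).

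**6. Scheduled safety data.** Visits for three months reach about week 12 or 13, leaving 24 − 13 = 11 to 24 − 12 = 12 weeks, or 46% to 50% of follow-up, without assured visits.

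**The case against.** The strongest reply is that the plan already protects safety data. A reader might infer that withdrawal removes the data of participants with events, so that one related grade 3 event in 10 would be reported as none in 9 (one-sided 95% upper bound 28.3% instead of 39.4%), or one in 5 as none in 4 (52.7% instead of 65.7%). The documents do not support that. The event is recorded and followed, and Section 8.1 keeps participants given both antibodies in the safety population. Nor is it right to say that a week-4 withdrawal forfeits 20 of 24 weeks of safety data, because Section 8.4 offers visits to about month 3. Both replies stand, with three limits: the visits are by invitation, the term used for drop-outs may not cover investigator withdrawals, and the safety population read literally requires both antibodies.

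Non-replacement is not a fault in itself, since it stops participants with events being swapped for others. Items 3 and 4 are not triggered by events, so the selective loss comes from item 2, or from item 5 used in the same way.

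Withdrawal also has a function after day 0: it ends burdensome procedures. Section 6.2.10 allows up to 100 mL of blood per follow-up visit, and Section 3.8 reports two grade 3 hemoglobin declines with 10-1074-LS. That is a good reason to keep clinical discretion. It is not a reason for ending a burdensome schedule to end all PK and ADA sampling as well.

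Finally, Section 8.1 calls the study exploratory and mainly descriptive, the rule is permissive, and Section 3.8 reports no related grade 3 or serious events with the LS antibodies so far. These limit the weight of the point but do not remove it.

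**Conclusion.** The concern holds in a limited form. Items 2 and 5 of Section 6.1.6.2 allow a dosed participant to be withdrawn from the whole study after an adverse event, when no study drug remains to be given. The exception, an event during the infusions, is covered by Section 6.1.6.1. The possible loss is post-withdrawal PK and ADA data, HIV-1 RNA if withdrawal is before week 4, and scheduled safety data from about month 3 to week 24.

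One case truncates the PK and ADA profile of 10% to 20% of the sample. How much of the elimination phase is missed depends on the half-life in viremic people, which the documents do not give for the LS antibodies. Across the range shown, 51% to 81% of antibody is still present at week 4. The number of such withdrawals is also not given, so no expected bias can be calculated. This is a cheap improvement that protects a primary and a secondary outcome. It is not a flaw that invalidates the safety analysis.

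**What to change.** Keep the investigator's and the provider's discretion to end burdensome procedures. Add to Section 6.1.6.2, for items 2 to 5 as they concern the investigator or provider, that a dosed participant who still consents is first offered reduced follow-up through week 24 before full withdrawal is accepted. The reduced visits would comprise safety laboratories, PK and ADA serum, and HIV-1 RNA through week 4. Item 5 must be included, or the same route stays open.

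Align Section 8.4 by replacing its safety-only visits with these reduced visits, and make clear that they cover investigator withdrawals as well as drop-outs.

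The cost is a wording amendment, site training and a few extra serum samples at reduced visits, within the blood-volume limit in Section 6.2.10. No extra participants are needed, and item 1 still lets anyone leave at any time.
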